Appendix K_Asthma Appendix K_Asthma Appendix K_Asthma
phenotypes and enphenotypes and enphenotypes and en

Diagnosing Comorbidities Associated with Asthma

Appendix
K_Diagnosing comoK_Diagnosing comoK_Diagnosing como

Inhaler Selection and Technique Training

Appendix K_Inhaler Appendix K_Inhaler Appendix K_Inhaler
selecting and techniselecting and techniselecting and techni

Systematic Approach to Spirometry

Appendix
K_Systematic approa

APPENDIX L. ASTHMA CLINIC EXPERIENCE (ACE) QUESTIONNAIRE (ENGLISH VERSION)

ASTHMA CLINIC EXPERIENCE (ACE) QUESTIONNAIRE

During your visit, you filled out the **Asthma Impairment and Risk Questionnaire (AIRQ™)**. Please answer the following questions, keeping in mind how your answers to the AIRQ™ may have affected your clinic experience.

	Strongly Agree	Agree	Disagree	Strongly Disagree	Not Applicable
1. The AIRQ™ helped me discuss my asthma with my health care provider(s).					
2. I received information about my asthma that helped me better understand my condition.					
3. I received information about my asthma medications.					
4. My health care provider(s) explained the results of tests that I have taken for my asthma.					
5. I was told the reason why tests for my asthma were ordered.					
6. I was given information about additional care that I need for my asthma.					
7. I was included in making decisions about my asthma treatment.					
8. The time spent with my health care provider(s) today discussing my asthma was better compared to my last visit.					

Please provide any additional comments you have about your visit or AIRQ™:

©2020 AstraZeneca. All rights reserved. US-45055 10/20

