5. STATISTICAL ANALYSIS PLAN

5.1 Statistical Methods – General Aspects

Descriptive statistics (n, frequency, mean, SD, median, range) will be used to characterize the sample in terms of sociodemographic and clinical characteristics and to summarize qualitative outcomes. These characteristics will be summarized for the sample overall, as well as for each site and cluster.

Additional analyses, including various subgroup analyses, to aid in the interpretation of the defined outcome measures may also be conducted and will be described in the Statistical Analysis Plan.

5.1.1 Primary Objective(s): Assess the Process and Potential Benefit of Implementing the AIRQ™, Asthma Checklist, and Educational Resources (PRECISION program) into Clinical Practice during Telehealth and In-Person Visits

Descriptive statistics (n, frequency, mean, SD, and 95% confidence intervals [Cis]) will be used to assess the process and potential benefits when integrating the AIRQ™ on a telehealth and in-person platform. Qualitative interviews will be summarized based on the interviewers' notes and the transcribed interviews. Findings from the touchpoint discussions with sites will be integrated into the qualitative findings. Audio recordings of interviews from clinical site personnel will be referred to as necessary to supplement interviewer notes and transcriptions. The interview results will be summarized in tabular format, with key recommendations, advantages, and disadvantages grouped accordingly. Specifically, barriers, benefits, challenges, ease of implementation, and areas for improvement will be summarized. Lastly, the results from the Post-study Survey will be summarized using descriptive statistics.

5.1.2 Secondary Objective(s): To Assess Patient Visit Satisfaction When the AIRQ™ Is Initiated as Part of a Telehealth or In-Person visit with Their HCP

To assess patient satisfaction with the AIRQ™, descriptive statistics (n, frequency, mean, SD, and 95% CIs) will be used to summarize patients' responses to the ACE Questionnaire.

Subgroup analysis may be conducted to examine responses by site, cluster, platform used, or AIRQ™ score.

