- During the visit, how was the AIRQ™ administered?
 Interviewer Patient self-completed
- During the visit, was the patient able to see their risk score on the ruler included in the AIRQ™?
 Yes No

IF yes, how were patients able to view their risk score?

On their phone
 On their computer
 Paper copy of AIRQ™ mailed to patient before the visit or provided at in-person visit
 Other, please specify: _____

- Age (years): 

Evidera 138	Site	Page 3 of 7
		
Evidera # 138	Plate # 003	Visit # 001
Participant ID		

5. Sex: male female non-binary Other: _____

6. How would you rate this patient's asthma severity?
 Intermittent
 Mild persistent
 Moderate persistent
 Severe persistent

[figure not shown]
7. Age of asthma diagnosis:  Unknown

8. What is your assessment of the patient's overall asthma control?
 Completely controlled
 Well controlled
 Somewhat controlled
 Poorly controlled
 Not controlled

9. Did the patient previously have COVID or do they currently have COVID?
 Yes No Unknown

10. What type of health insurance coverage does the patient have? (Check all that apply)
 Third-party payer (for example, United Healthcare, Blue Cross/Blue Shield, Aetna)
 Managed care organization
 Tricare (military health insurance)
 Affordable Care Act (ACA)
 Medicare
 Medicaid
 Self-pay
 None
 Other (please specify): _____

11. Patient's state of residence: 

Evidera 138	Site	Page 4 of 7
		
Evidera # 138	Plate # 004	Visit # 001
Participant ID 		

12. Please indicate the medication the patient has taken for the past 3 months:

[figure not shown]
MAINTENANCE PHARMACOLOGIC THERAPY Please check all that apply .	

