1.2 Secondary Objective

The secondary objectives of this study are:

1. To assess clinic visit experiences of patients with asthma and when the AIRQ®, Asthma Checklist, and educational resources (PRECISION program) are utilized as part of a telehealth or in-person visit with their HCP
2. To explore change in AIRQ® scores from the initial visit to follow-up visit(s) (when available)

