visit will also be summarized by visit platform (telehealth vs. in-person), exacerbation history, education level, language, age, sex and NAEPP step level (Table 10b to 10h). In Table 10i, descriptive statistics (mean, SD, median, range) will be used to detail the average number of AIRQs® completed by patients overall and in each practice cluster. In Table 10j, AIRQ® scores from the patient's final follow-up (if more than 1 follow-up AIRQ) will be summarized.

5.1.1 Primary Objective: Assess the Process and Potential Benefits of Implementing the AIRQ™, Asthma Checklist, and Educational Resources (PRECISION Program) into Clinical Practice

This analysis will be conducted on the HCP analysis set of clinicians who completed the post-study survey. Descriptive statistics (n, %) will be used to summarize the proportion of responses for each of the categorical items on the post-study survey (e.g., How would you rate the overall ease of implementing the AIRQ™ into your clinical practice using the telehealth platform?). Descriptive statistics (mean [SD], median, range) will be used to summarize the number of patients treated using the PRECISION program (Table 11). Results will be presented overall and by practice cluster.

Qualitative analyses will be conducted to evaluate the frequency of descriptive free-text responses to open-ended questions on the post study survey (e.g., What features of the PRECISION program do you think could be improved?) (Table 12 series), from the qualitative interviews with key site staff and clinicians (Table 13 series), and from the implementation touchpoint calls with key site staff and clinicians (Table 14 series).

5.1.2 Secondary Objective(s): 1) To Assess Patient Visit Satisfaction When the AIRQ™ Is Initiated as Part of a Telehealth or In-Person visit with Their HCP; 2) To explore change in AIRQ® scores from the initial visit to follow-up visit(s)

To assess patient satisfaction with AIRQ®, descriptive statistics (n, %) will be used to summarize patient responses to the ACE Questionnaire overall and by practice cluster (Table 7a). Scores will also be summarized by visit platform (in-person vs. telehealth), AIRQ® control level, education level, age, exacerbation history, and patient language (Table 7 series).

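### Protocol 5.1.2 and SAP 5.1.2 present the ACE summary as satisfaction with the AIRQ, but only item 1 of its eight rated items names the AIRQ and no comparator ties the other seven to it

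*Protocol*

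**What the plan says.** The documents describe what the ACE Questionnaire measures in three ways.

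- **Objective.** SAP 1.2 begins secondary objective 1 with "To assess clinic visit experiences of patients with asthma" and sets it in visits where the AIRQ, the Asthma Checklist and the educational resources are all used. Protocol 2.2 has the same objective.
- **Outcome definitions and section headings.** Protocol 4.2.2 and SAP 4.2.2, and the headings of 5.1.2 in both documents, speak of satisfaction with a visit in which the AIRQ is initiated.
- **Analysis sentences.** Protocol 5.1.2 opens with "To assess patient satisfaction with the AIRQ™, descriptive statistics". SAP 5.1.2 says "To assess patient satisfaction with AIRQ®, descriptive statistics (n, %) will be used to summarize patient responses to the ACE Questionnaire overall" and by practice cluster. Here the object of satisfaction is the AIRQ itself.

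The questionnaire is in Protocol Appendix L. Its lead-in asks patients to answer "keeping in mind how your answers to the AIRQ™ may have affected your clinic experience". Item 1 begins "The AIRQ™ helped me discuss my asthma with my health care provider(s". No other rated item mentions the AIRQ. A closing open question invites comments on the visit or the AIRQ.

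SAP Appendix A says the ACE has no total score and that each item is described by frequency. SAP 4.1.3.1 has all participants complete the AIRQ at the initial visit. The Protocol synopsis and Protocol 6.1.2 list the ACE for the initial visit only.

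**The concern.** The analysis sentence is narrower than the objective it serves, and it names something the questionnaire mostly does not ask about. A patient who was told about medications will agree with item 3 whether or not the AIRQ prompted the conversation. A good visit and a useful AIRQ can produce the same answers to items 2-7.

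The design does not separate the two. Every respondent had the AIRQ, and the Checklist and educational resources belong to the same program. Even a real effect of the program could not be assigned to the AIRQ from these items.

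What is at stake is the conclusion drawn for a secondary objective. Wording carried from the analysis section into a table title or report would credit the sponsor's tool with results that describe the visit. The documents do not warn of this. The bias text in Protocol 5.2.1 and SAP 6.1 covers optional response to the ACE and selection of patients with follow-up, and Protocol 5.2.3 covers generalisability. Neither mentions the missing comparator.

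**Working it through.** **1. Count the items.** Appendix L has eight rated items and one open comment, and SAP 4.1.3.3 agrees. Protocol 4.1.9 and 4.2.2 count nine. I use the eight that are printed.

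| ACE item | What it asks | Names the AIRQ? |
|---|---|---|
| 1 | Whether the AIRQ helped discussion with the provider | Yes |
| 2-3 | Whether information on asthma and on medications was received | No |
| 4-5 | Whether test results, and reasons for tests, were explained | No |
| 6 | Whether information on further care was given | No |
| 7 | Whether the patient shared in decisions | No |
| 8 | Whether time spent was better than at the last visit | No |

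Items naming the AIRQ: 1/8 = 12.5%. Items not naming it: 7/8 = 87.5%.

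**2. Look for a comparator.**
- Patients without the AIRQ: none (SAP 4.1.3.1). The web-survey analysis set in SAP 3 is drawn from enrolled patients who completed the initial visit.
- ACE before the AIRQ: none. Protocol 6.1.2 mentions asking about a survey at 3 months as well, but that too would come after the AIRQ.
- Planned ACE groupings in SAP 5.1 are cluster, platform, AIRQ control level, exacerbation history, education, language, age, sex and NAEPP step. Each compares AIRQ-exposed patients with one another. SAP Appendix B later drops language.
- Item 8 has a built-in comparison with the last visit, but anything else that differed between the two visits could explain the answer.

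**3. What follows.** For any of items 2-7, let p be the observed agreement and b the agreement the same patients would have given without the AIRQ. The AIRQ's contribution is p - b. The study estimates p and never observes b.

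The documents give no ACE rates, so these values are assumptions that show the structure, not a forecast. With p = 90%:
- b = 50% gives 90 - 50 = +40 points
- b = 70% gives 90 - 70 = +20 points
- b = 90% gives 90 - 90 = 0 points

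**4. Precision does not help.** The planned total of about 750 to 1,500 reproduces as 15 sites x 50 = 750 and 20 sites x 75 = 1,500. The 95% half-width for one proportion is 1.96 x sqrt(p(1-p)/n). At p = 0.9:
- n = 750 (everyone responds): 1.96 x sqrt(0.09/750) = 2.1 points
- n = 225 (assumed 30% response, 0.30 x 750): 1.96 x sqrt(0.09/225) = 3.9 points

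The 95% confidence intervals that Protocol 5.1.2 plans would describe agreement well and say nothing about b.

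**The case against.** The strongest reply is that the phrase is an isolated lead-in. The headings above it, the outcome definitions and the objectives all stay at the level of the visit. The SAP repeats the Protocol's sentence, so it has not drifted from it. This stands, and it makes the repair easy. It does not make the sentence correct, because that sentence states what the ACE summary is meant to assess.

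Second, the lead-in connects every item to the AIRQ, and the open question is another AIRQ-specific source. This stands in part. The lead-in gives loose self-attribution, but most items can be answered truthfully without regard to it. The free-text comments deserve a place beside item 1.

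Third, the study is declared descriptive and makes no causal claim for the ACE. That is true, and no comparator needs to be added. A descriptive result still needs the right name.

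A reader might go further and infer that the report would show a high rate of AIRQ satisfaction even if the AIRQ did nothing. The documents do not support this. No such rate is defined, there is no total score, and a result on medication information would appear as that item. Nor do they give any figure for agreement after an ordinary visit.

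A reader might also infer that the Clinical CRF question "During the visit, was the patient able to see their risk score on the ruler included in the AIRQ™" could isolate the AIRQ's contribution if used as a grouping factor. It could not. Protocol 3.1 and SAP 2 have providers discuss the AIRQ results with patients, with no condition that the ruler was seen, so a patient who did not see it is not unexposed. The viewing routes are phone, computer or paper, so the answer is probably tied to visit platform. SAP Appendix B describes completed analyses, so the contrast would also be post hoc.

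**Conclusion.** The point holds as a mislabelled inference in one sentence of each document. Seven of the eight rated items cannot support a statement about satisfaction with the AIRQ. Item 1 and AIRQ-related comments can support a limited one, about whether patients found it helpful.

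This rests on the printed wording of Appendix L, on universal completion of the AIRQ, and on the absence of an ACE baseline. It does not depend on any assumed agreement rate.

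The consequence is modest. Item-level reporting lets item 1 be read alone, and no planned statistic, sample size or test changes. What changes is the conclusion that secondary objective 1 can carry: visit experience under the PRECISION program, with one rated item that speaks to the AIRQ.

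**What to change.** - In Protocol 5.1.2, replace the purpose given as "To assess patient satisfaction with the AIRQ™" with patient visit experience when the PRECISION program is used. Make the same change in SAP 5.1.2. This brings both sentences into line with secondary objective 1.
- Limit AIRQ-specific conclusions to ACE item 1 and to free-text comments about the AIRQ.
- Report items 2-8 as visit experience, without attributing them to the AIRQ.
- Add to the ACE limitations in Protocol 5.2 and SAP 6.1 that there was no visit without the AIRQ and no ACE baseline, so the AIRQ's contribution cannot be separated from the rest of the visit or program.

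The cost is a few lines of text. No new data, table or analysis is needed. If the report is already drafted, the same wording belongs in its table titles and discussion. The one downside is a more modest claim about the AIRQ.

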APPENDIX M. ASTHMA CLINIC EXPERIENCE QUESTIONNAIRE (SPANISH VERSION)

CUESTIONARIO SOBRE LA EXPERIENCIA CLÍNICA CON EL ASMA (ASTHMA CLINIC EXPERIENCE, ACE)

Durante su visita, usted completó el **cuestionario sobre el daño y el riesgo del asma (Asthma Impairment and Risk Questionnaire, AIRQ™)**. Responda a las siguientes preguntas, teniendo en cuenta cómo sus respuestas en el AIRQ™ pueden haber afectado su experiencia clínica.

	Muy de acuerdo	De acuerdo	En desacuerdo	Muy en desacuerdo	No corresponde
1. El AIRQ™ me ayudó a hablar sobre el asma con mi(s) proveedor(es) de cuidados de la salud.					
2. He recibido información sobre el asma que me ha ayudado a comprender mejor mi condición.					
3. He recibido información sobre mis medicamentos para el asma.					
4. Mi(s) proveedor(es) de cuidados de la salud me explicó/ explicaron los resultados de las pruebas que me he realizado para mi asma.					
5. Me han explicado el motivo por el que se solicitaron pruebas para mi asma.					
6. Me dieron información sobre la atención adicional que necesito para mi asma.					
7. Me incluyeron al momento de tomar decisiones sobre el tratamiento para mi asma.					
8. El tiempo que pasé hoy con mi(s) proveedor(es) de cuidados de la salud hablando sobre el asma fue mejor comparado con mi última visita.					

Por favor proporcione cualquier comentario adicional que tenga sobre su visita o el AIRQ™:

Observational Study Protocol
Study Code D2287L00028 [EVA-26645-03]
Version 2.0
Date June 16, 2022

Observational Study Protocol Form
Version 3.0
Form Doc ID: AZDoc0059948
Parent Doc ID: SOP LDMS_001_00164328

Observational Study Protocol
Study Code D2287L00028 [EVA-26645-03]
Version 2.0
Date June 16, 2022

CCI

Observational Study Protocol Form
Version 3.0
Form Doc ID: AZDoc0059948
Parent Doc ID: SOP LDMS_001_00164328

Observational Study Protocol
Study Code D2287L00028 [EVA-26645-03]
Version 2.0
Date June 16, 2022

CCI

Observational Study Protocol Form
Version 3.0
Form Doc ID: AZDoc0059948
Parent Doc ID: SOP LDMS_001_00164328

Observational Study Protocol
Study Code D2287L00028 [EVA-26645-03]
Version 2.0
Date June 16, 2022

Placeholder

Observational Study Protocol Form
Version 3.0
Form Doc ID: AZDoc0059948
Parent Doc ID: SOP LDMS_001_00164328

APPENDIX R. PATIENT SOCIODEMOGRAPHICS QUESTIONNAIRE (ENGLISH VERSION)

Please complete all questions, if possible.

1. *What is your age?* _____ years

2. *What is your sex?*
 male female non-binary Other: _____

3. *What is your ethnic background?*
 Hispanic or Latino
 Not Hispanic or Latino

4. *What is your racial background? (Please mark all boxes that apply with an “X.”)*
 White
 Black or African American
 Asian
 Native Hawaiian or other Pacific Islander
 American Indian or Alaska Native
 Other (specify): _____

5. *What is your current living/domestic situation? (Please mark only one box with an “X.”)*
 Living alone
 Living with a spouse, partner, family, or friends
 Other (specify): _____

6. *How would you describe your employment status? (Please mark only one box with an “X.”)*
 Employed, full-time
 Employed, part-time
 Homemaker
 Student
 Unemployed
 Retired
 Disabled
 Other (specify): _____

7. *What is the highest level of education you have completed? (Please mark only one box with an "X.")*

- Less than high school
- Secondary/high school
- Associate degree, technical or trade school
- College/university degree
- Postgraduate school
- Other (specify): _____

8. What is your household's total income from all sources over the past 12 months?

- Less than \$15,000
- \$15,000 to \$29,999
- \$30,000 to \$44,999
- \$45,000 to \$59,999
- \$60,00 to \$74,999
- \$75,000 to \$99,999
- \$100,000 or more
- Prefer not to answer

9. *How old were you when you were diagnosed with asthma? _____*

10. *Do you smoke?*

- Yes, current smoker
- Not currently, but previous smoker
- No, never smoked

Observational Study Protocol
Study Code D2287L00028 [EVA-26645-03]
Version 2.0
Date June 16, 2022

APPENDIX S. PATIENT SOCIODEMOGRAPHICS QUESTIONNAIRE (SPANISH VERSION)

Placeholder

APPENDIX T. CLINICAL SITE TOUCH POINT QUESTIONS

1. Please describe how the PRECISION Program is being implemented at your site?
2. What aspects of study implementation are going well for your site? Telehealth vs in-person?
3. What aspects of study implementation have been challenging for your site? Has the site experienced any barriers to implementing the PRECISION program? Telehealth vs in-person?
4. Please describe any site-level factors (e.g., site operations, clinical team) that have affected the implementation of the PRECISION Program on a telehealth platform at your site? During an in-person visit?
5. What could be done to help overcome these site-level challenges and support the use of the PRECISION Program on a telehealth platform at your site? During an in-person visit?
6. Please describe any participant-level factors that have affected the implementation of the PRECISION Program on a telehealth platform at your site? During an in-person visit?
7. Based on your experiences to date, does your site plan to make any changes or adapt how the PRECISION Program is currently being implemented on a telehealth platform at your site? During an in-person visit?

APPENDIX U. POST-STUDY SURVEY

PART 1. INFORMED CONSENT

PART 2. POST-STUDY SURVEY

1. Approximately how many patients have you treated using the PRECISION Program?

2. Which visit type best describes how the majority of your initial patient visits took place?
 Telehealth visit (approximately ____ %)
 In-person visit (approximately ____ %)
3. How would you rate the overall ease of implementing the AIRQ™ into your clinical practice using the telehealth platform?
 Very easy
 Somewhat easy
 Difficult
 Very Difficult
4. How would you rate the overall ease of implementing the AIRQ™ into your clinical practice during an in-person visit?
 Very easy
 Somewhat easy
 Difficult
 Very Difficult
5. Did the AIRQ™ help you manage your patients?
 Yes, very much
 Yes, somewhat
 Not at all
6. Regardless of intermittent or persistent, on average, what percentage of your asthma patients would you classify as:
____ % Mild asthma
____ % Moderate asthma
____ % Severe asthma
= 100%

7. Did AIRQ™ help you identify patients who were at risk for adverse health outcomes (e.g., hospitalizations, exacerbations, medication side effects) from their asthma that you would have otherwise missed?

- Yes
- No

8. What did you find most useful about AIRQ™?

- Total AIRQ™ score
- Questions on impact/impairment (#1-6)
- Question on control (#7)
- Questions on exacerbations and healthcare resource utilization (#8-10)

9. What did you find least useful or cumbersome about AIRQ™?

- Total AIRQ™ score
- Questions on impact/impairment (#1-6)
- Question on control (#7)
- Questions on exacerbations and healthcare resource utilization (#8-10)

10. Did AIRQ™ improve any of the following: *Check all that apply*

- Increased recognition of patients whose asthma placed their health at risk
- Increased recognition of conditions/risks, comorbidities driving poor asthma control
- Improved recognition of patient goals
- Improved patient engagement with their treatment, risk, or control
- Improved efficiency of patient telehealth visit
- Improved efficiency of in-person asthma clinic visit
- Increased educational efforts

11. While using AIRQ™, how often did you refer to a specialist or practice type different than your own?

- No different than if I did not have the tools
- More often than before
- Less often than before

12. What features of the PRECISION program did you find most useful?

13. What features of the PRECISION program do you think could be improved?

14. How important was it for you to use the Assess component of the Asthma Checklist (page 1) with the AIRQ?

Very important
 Somewhat important
 Not at all important
 Did not use

15. How important was it for you to use the Adjust and Review components of the Asthma Checklist (pages 2 and 3)?

Very important
 Somewhat important
 Not at all important
 Did not use

16. How important do you feel it would be for PCPs to use the Assess component of the Asthma Checklist (page 1) with the AIRQ?

Very important
 Somewhat important
 Not at all important
 Did not use

17. How important do you feel it would be for Specialists to use the Adjust/Review pages of the Asthma Checklist with the AIRQ?

Very important
 Somewhat important
 Not at all important
 Did not use

18. How important do you feel it would be for Non-prescribers to use the Assess component of the Asthma Checklist (page 1) with the AIRQ?

Very important
 Somewhat important
 Not at all important
 Did not use

19. Do you have any other comments or suggestions?

